**“Effect of Propolis or Metformin Administration
on Glycemic Control in Patients With Type 2
Diabetes Mellitus”**

NCT03416127

April 6, 2017

Effect of Propolis or Metformin Administration on Glycemic Control in Patients With Type 2 Diabetes Mellitus

INTRODUCTION

Type 2 Diabetes Mellitus (DM2) is a health problem that has reached alarming levels, as currently, about half a billion people suffer from it around the world. For 2019, a total of 463 million was estimated and an increase of 51% is expected by 2040.¹ It is a disease characterized by dysfunction of beta cells, hepatic glucose metabolism and peripheral insulin resistance, a state in which tissues sensitive to it show a decreased response to normal insulin levels.²

The first-line treatment in newly diagnosed patients is metformin, mainly due to its efficacy in reducing glycemic control, safety profile, and weight neutrality.^{3,4} However, this depends on factors such as treatment compliance, access to medicines, counseling, regular monitoring of blood sugar levels, access to health care services, and quality of management. To date, a significant number of people around the world use complementary and alternative medicine (CAM) to treat chronic diseases, with reports of 64%. Of these, 35.5% use CAM for DM2.⁵

Propolis, is a natural product produced by the bee *Apis mellifera* by adding salivary secretions (β -amylase) and wax to the balsamic resinous material, which they collect from shoots, exudates of trees and other parts of the plants as lipophilic materials in the leaves, mucilages, gums, resins, latex, etc. Etymologically the term propolis, comes from the Greek and means in “defense of the city (or beehive)”.⁶⁻⁹ It has been known and used since ancient times by offering options such as antimicrobial, anti-inflammatory, antioxidant, antitumor, antiulcer, anesthetic, hepatoprotective and healing therapy.^{6,10,11} It is composed of flavonoids, terpenes, phenolic acids, as well as proteins, sugars, vitamins and abundant minerals.^{10,11}

Recent studies have shown the efficacy of propolis on the reduction of fasting glucose and glycated hemoglobin,^{9,12,13} insulin resistance^{13,14} and postprandial glucose.¹⁴ However, there is a controversy between some results, as Fukuda et al. indicated that there was no significant difference in the parameters of glycemic control and insulin resistance.¹⁵ Likewise, Zakerkish et al. found no relevant reduction in fasting glucose after propolis supplementation.¹⁴

Therefore, there is a need for further studies, as there is no evidence from studies evaluating the effect of propolis on glycemic control in newly diagnosed patients without drug treatment. In addition to this, it has not been compared to the gold standard, metformin. Our hypothesis is that the administration of propolis or metformin modifies glycemic control in newly diagnosed patients without pharmacological treatment. The objective of this study is to evaluate the effect of propolis or metformin administration on glycemic control in recently diagnosed patients without pharmacological treatment.

MATERIAL AND METHODS

Selection criteria

Patients with a diagnosis of DM2 less than 5 years old and without pharmacological treatment for at least 3 months before entering the study, 30 to 60 years of age, mild to moderate physical activity, stable body weight for at least 3 months before the study, body mass index (BMI) of 25.0 to 34.9 kg/m², fasting serum glucose <13.88 mmol/L and postload serum glucose >11.10 mmol/L, will be criteria for entering the study. For the selection of individuals diabetes detection campaigns will be carried out in the metropolitan area of the City of Guadalajara. Women in the reproductive stage at risk of pregnancy, subjects who consumed drugs or supplements that modify the behavior of DM2, personal history of cardiovascular, kidney, pancreatic or thyroid disease and/or uncontrolled systemic arterial hypertension, known allergies to bee's sting or its derivative products, intolerance to metformin, total cholesterol (TC) \geq 6.20 mmol/L, triglycerides (TG) \geq 4.48 mmol/L will be excluded. Individuals with lack of tolerability to propolis, metformin and/or placebo, with adherence to treatment <80%, in the presence of a serious adverse event and/or who withdrew informed consent will be eliminated.

Study design

A randomized, double-blind, placebo-controlled clinical trial of three pharmacological groups will be carried out, with the participation of 34 patients with a recent diagnosis of DM2 according to the criteria of the American Diabetes Association.¹⁶ The propolis capsules

will be obtained from NOW® of Chicago, Illinois (USA), containing 300 mg of propolis powder. Calcined magnesia will be used for the placebo. The allocation will be done by simple randomization using a list of numbers. All patients will receive for 12 weeks one capsule before the first bite of breakfast and another before the first bite of dinner. 12 of them took propolis (300 mg twice a day), another 12 received metformin (850 mg twice a day) and 12 more, placebo in the same pharmacological presentation. Each participant will receive medical nutritional therapy and will be instructed to continue with their normal physical activity.

Clinical and laboratory measurements

The medical history of each patient will be taken and anthropometric indices will be measured that included: height, weight, BMI, waist circumference (WC) and percentage of fat mass. In addition to blood pressure. Five visits will be completed during the study and a 2-h oral glucose tolerance test (OGTT) will be performed at the beginning and end of the intervention to calculate the areas under the curve (AUC) of glucose and insulin, total insulin secretion (insulinogenic index), first phase of insulin secretion (Stumvoll index) and insulin sensitivity (Matsuda index). For this, the individuals will take a solution with 75 g of anhydrous glucose dissolved in 300 ml of water in 5 minutes. After that, blood samples will be taken through a heparinized catheter before and at 30-min intervals (30, 60, 90 and 120 minutes) for 2 hours. At each visit, the presence of adverse events will be verified through the diary and compliance through the capsule count.

Laboratory tests will be performed at 8:00 a.m. after an overnight fast from 10 to 12 h. Body weight will be evaluated by bioimpedance with a digital scale (Tanita®), with the participant in a standing position and wearing light clothing, without footwear and with the bladder evacuated before the measurement. For height, subjects will be asked to remove their shoes and stand with their feet together; measurements will be rounded to the nearest centimeter. WC will be taken at the midpoint between the highest point of the iliac crest and the lowest rib on the midaxillary line to the nearest centimeter. Percentage of fat mass will be evaluated through bioimpedance. BMI will be calculated as weight (kg) divided by height (m²). A digital sphygmomanometer (Omron Hem-907 XL®) will be used to determine blood

pressure, and the mean value of three measurements will be recorded after a 5-min rest period.

Venous blood samples will be obtained and kept at room temperature for 30 min. The samples will be centrifuged and the serum will be placed in three aliquots; one will be used immediately for the measurement of fasting glucose, glycated hemoglobin A1c (A1C), TC, TG, high-density lipoprotein cholesterol (HDL-c), uric acid and creatinine, and the rest will be frozen at -20 °C for the determination of insulin. All biochemical measurements will be calculated with enzymatic colorimetric methods on an automatic analyzer (Erba XL-100®) with BioSystems S.A. reagents. Insulin concentrations will be measured with the enzyme-linked immunosorbent assay (ELISA) technique using the kit (DRG, Inc).

To calculate low-density cholesterol, the Friedewald formula will be used: $LDL-c \text{ (mmol/L)} = TC \text{ (mmol/L)} - HDL-c \text{ (mmol/L)} - [TG \text{ (mmol/L)} / 2.2]$, while for very low density cholesterol (VLDL) the ratio of $TG \text{ (mmol/L)} / 2.2$ will be used. With a liquid chromatography the percentage of A1C will be calculated. The AUC of glucose and insulin will be calculated with the polygonal formula. Total insulin secretion will be assessed with the insulin index: $(\Delta AUC \text{ of insulin}) / (\Delta AUC \text{ of glucose})$. With the Matsuda $10000 / \sqrt{[(Glucose_0 \cdot Insulin_0) (Average \text{ of the PTOG} \cdot Average \text{ of the insulin in the PTOG})]}$ index the insulin sensitivity will be estimated, while with the index from Stumvoll $1283 + 1.829 \times \text{insulin}_{30'} - 138.7 \times \text{glucose}_{30'} + 3.772 \times \text{insulin}_0'$, the first phase of insulin secretion.

Sample size

For this study, the sample size it's calculated using a formula for mean difference¹⁷ with a statistical confidence of 95%, a statistical power of 80%, a standard deviation (SD) and an expected difference for fasting glucose, A1C and 2-h glucose of 0.6 mmol/L¹² and 1.0 mmol/L⁹, 0.5% and 0.8%¹², 2.3 mmol/L¹⁸ and 3.9 mmol/L¹⁹, respectively. While for metformin it's of 2.4 mmol/L²⁰ and 3.0 mmol/L²¹, 1.0% and 1.5%²², 3.5 mmol/L²³ and 5.5 mmol/L²⁴, respectively. A total of 12 patients is obtained for each group, including 20% of the expected loss.

Security measures

All patients will be informed about the possible adverse effects of propolis and metformin; they will have the emergency telephone numbers of the responsible and associated investigators.

STATISTIC ANALYSIS

The study will be designed to demonstrate the effect of propolis and metformin relative to placebo in terms of the outcome variables of effectiveness. Assuming there are no differences in propolis and metformin versus placebo regarding effectiveness in reducing glycemic control, it's calculated that approximately 36 randomized patients will provide ~80% power to demonstrate superiority.

All statistical analyzes will be performed by intention to treat, which will be included randomized patients who receive at least 1 dose of study treatments and for whom there has a baseline value on measurements. First, with the Kruskal-Wallis test, it will be tested whether the baseline data group of primary and secondary variables come from the same population, that is, whether the 3 groups are comparable as no statistically significant differences are found.

Then, using the Kruskal-Wallis test, the final data will be evaluated and with those that will be significant a post-hoc test (Mann Whitney U) will be performed, comparing propolis versus metformin, propolis versus placebo, and metformin versus placebo. Differences between baseline and final measurements for primary and secondary variables will be calculated with the Wilcoxon test. Statistical comparisons will be made using a comparative type 1 error of 5% (two-tailed).

The safety profile analysis will include patients who receive at least 1 dose of study medication; safety data will be summarized using descriptive statistics.

FINANCING

The financing will be by own resources of the University of Guadalajara.

REFERENCES

1. IDF (International Diabetes Federation). International Diabetes Federation. Vol. 9, International Diabetes Federation. 2019. 144 p.
8. Khalil M. Biological activity of bee propolis in health and disease. *Asian Pac J Cancer Prev APJCP.* 2006;7:22–31.

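### Patients are to be eliminated for events after randomisation without saying from what; two of the three possible meanings undermine the intention-to-treat analysis, one in its wording and one in practice

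*Combined protocol and SAP*

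**What the plan says.** The last sentence of Selection criteria in the combined protocol and SAP begins "Individuals with lack of tolerability to propolis, metformin and/or placebo" and continues "with adherence to treatment <80%, in the presence of a serious adverse event and/or who withdrew informed consent will be eliminated". It names four triggers (intolerance, low adherence, serious adverse event, withdrawn consent) and gives no object for the verb.

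Statistic analysis defines the efficacy set: "All statistical analyzes will be performed by intention to treat, which will be included randomized patients who receive at least 1 dose of study treatments". The only other requirement is a baseline measurement. The section sets no condition on adherence, tolerability, adverse events or the presence of a final value. The safety set is every patient with one or more doses.

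The efficacy tests use end-of-treatment data: "using the Kruskal-Wallis test, the final data will be evaluated", then "with those that will be significant a post-hoc test (Mann Whitney U) will be performed", and "Differences between baseline and final measurements for primary and secondary variables will be calculated with the Wilcoxon test". Under Clinical and laboratory measurements, the glucose tolerance test "will be performed at the beginning and end of the intervention"; the visits at which A1C and fasting glucose are drawn are not given. No per-protocol set and no rule for missing final values appears anywhere.

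**The concern.** The sentence stands under an eligibility heading, but its triggers arise after randomisation. Baseline criteria have their own verb (excluded), and known intolerance to metformin is already among them. Intolerance of placebo and poor capsule adherence can appear only once dosing has begun. No run-in is described, and adherence and adverse events are checked at the study visits.

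Who enters the main comparison therefore turns on one undefined word, in groups of 12. Two analysts could follow the document faithfully and analyse different patients, and the choice could be made after results are known. Because tolerability, adherence and serious adverse events can depend on the assigned treatment, taking such patients out can undo the protection of randomisation.

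**Working it through.** **1. The three meanings against Statistic analysis**

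| Eliminated from | Effect on the stated analysis |
|---|---|
| the analysis | Direct contradiction: the efficacy set has no such condition. If it applied to all analyses, removing patients with a serious adverse event would also conflict with the safety set. |
| the study (follow-up) | No contradiction in wording, since a final value is not required for membership. In practice the patient may have no final value, the Kruskal-Wallis and Wilcoxon tests cannot use the patient, and no missing-data rule applies. |
| study drug only | Compatible, but not stated. |

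**2. The plan's own sample size**

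Inputs from Sample size: two-sided 5%, power 80%, and each pair read as SD then difference, the order in which the text names them. Propolis: 0.6/1.0, 0.5/0.8, 2.3/3.9. Metformin: 2.4/3.0, 1.0/1.5, 3.5/5.5.

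Formula: n = 2 × [SD × (1.96 + 0.84)/difference]². The largest requirement is metformin fasting glucose: 10.05 per group. Then 10.05 × 1.2 = 12.06, in line with the stated 12. (Dividing by 0.8 gives 12.56; rounding up to 11 first gives 14.)

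**3. How large could the bias be? Illustration only**

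Assumptions not in the documents: standard normal outcomes, no drug effect, 12 per arm. Each patient in an affected arm is removed if a variable with correlation ρ to the outcome exceeds a fixed threshold, set so that 2 of 12 are removed on average. Kruskal-Wallis by chi-square with 2 df at 0.05, 200,000 samples per setting.

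| Arms affected | ρ = 0 | ρ = 0.5 | ρ = 1.0 (worst case) |
|---|---|---|---|
| One arm | 4.7% | 5.6% | 8.2% |
| Both active arms | 4.6% | 5.6% | 8.8% |
| All three alike | 4.5% | 4.6% | 4.6% |

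The mean of an affected arm shifts by ρ × φ(z)/(10/12), where z is the 10/12 quantile of the standard normal (0.967, φ = 0.250). That is 0.15 SD at ρ = 0.5 and 0.30 SD at ρ = 1. SD/difference runs from 2.3/3.9 = 0.59 to 2.4/3.0 = 0.80. The shift is therefore 9% to 12% of the planning differences at ρ = 0.5, and 18% to 24% at ρ = 1.

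**4. What keeping these patients could cost in power**

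Assume 2 of 12 active patients show no effect, so the mean difference is 10/12 of that planned.

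- Power = Φ[difference × (10/12)/(SD × √(2/12)) − 1.96]. Metformin fasting glucose: Φ(2.55 − 1.96) = 72%. The other five pairs: 86% to 93%.
- Counting the spread from mixing in non-responders, the active-arm variance is SD² + (10/12)(2/12) × difference². For metformin fasting glucose this is 5.76 + 1.25 = 7.01, and power is Φ[2.5/√((7.01 + 5.76)/12) − 1.96] = 68%. The other five pairs: 81% to 88%.
- For comparison, 12 full responders per group give 86.5% for metformin fasting glucose, and 10 give 79.8%.

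These are mean-difference formula values, not the power of the planned rank tests.

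**The case against.** The strongest reply is that Statistic analysis is the section that governs analysis, and it is clear. The elimination sentence sits among participation rules and never mentions analysis. Reading it as removal from the analysis would also clash with the safety set, so that is the least natural meaning. This stands in part: the conflict is conditional, and a reader who infers that the plan flatly contradicts its intention-to-treat statement goes further than the text allows. It does not remove the problem, because nothing says that patients who stop are followed to the end.

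A second reply is that removal from the study is only a missing-data gap, which any dropout would create. That too is fair: it is a different kind of defect from a contradiction, and after withdrawn consent some loss may be unavoidable. But here the plan itself may create the gap, by rule, for reasons that can be related to treatment.

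A third reply concerns size. A reader might infer that such removal roughly doubles the false-positive rate even when every arm loses patients alike. Forcing exactly the 2 worst of 12 out of each of the three arms does give 9.6%, but that comes from the fixed count, which makes the remaining values in an arm dependent. The plan's criteria apply patient by patient. Under a common patient-level threshold the surviving patients have the same distribution in every arm when there is no effect, and the error stays near 4.6%.

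Two further inferences are not supported. The 20% loss allowance fits any of the three meanings. The 34 participants given under Study design, against 12 + 12 + 12 = 36, are a separate inconsistency and do not show that two patients were eliminated.

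**Conclusion.** The point holds in conditional form, as a SHOULD-FIX. One undefined word leaves the main analysis set open. One meaning contradicts the intention-to-treat statement, one empties it in practice for want of final values and a missing-data rule, and one is compatible but unstated. The severity rests on that undetermined set, not on the error rates.

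The real size and direction of any bias cannot be derived from the documents. Under the assumed removal of 2 of 12 on average, moderately outcome-related removal changes little. Only removal that is both strongly outcome-related and unequal between arms raises the global error materially, to about 8% to 9%.

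**What to change.** Reconcile Selection criteria with Statistic analysis by stating, for each of the four triggers, whether study drug, follow-up or inclusion in the analysis ends. In particular:

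1. Patients who meet a criterion keep their assigned group and are asked to attend the planned final measurements, unless consent is withdrawn.
2. Their available final values enter the primary intention-to-treat analysis.
3. Adherence of at least 80% defines only a secondary per-protocol set.
4. The sponsor's statistician prespecifies one method for final values that are still missing.

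When study drug is stopped is a clinical matter and is not changed here.

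The cost is amended wording and a few extra final visits: about 6 if 2 of 12 per arm are affected (2 × 3). Power may fall, to about 68% to 72% by the formula for metformin fasting glucose; the other five pairs stay above 80%. If the sponsor wanted 80% for that one comparison under the same assumption, the formula gives 15 per group, or 17 with the added spread (16 gives 79.9%). If treatment only was meant, one sentence removes the ambiguity, but item 4 is still needed because withdrawn consent can leave gaps under any meaning.

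### The planned total is given as 34 in one place and 36 in others, and simple randomisation as named does not secure the 12 per arm that the sample size relies on

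*Combined protocol and SAP*

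**What the plan says.** The Study design section describes a "placebo-controlled clinical trial of three pharmacological groups", to be run "with the participation of 34 patients with a recent diagnosis of DM2". A few lines later it gives the arms: "12 of them took propolis (300 mg twice a day), another 12 received metformin (850 mg twice a day) and 12 more, placebo". It describes allocation in one sentence: "The allocation will be done by simple randomization using a list of numbers". No allocation ratio, block size or other restriction is stated.

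The Sample size section uses a formula for a difference in means, "with a statistical confidence of 95%, a statistical power of 80" per cent, and concludes: "A total of 12 patients is obtained for each group, including 20% of the expected loss". The Statistic analysis section says that "approximately 36 randomized patients will provide ~80% power to demonstrate superiority".

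**The concern.** There are two separate points.

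1. **The total.** Three arms of 12 make 36, so a total of 34 contradicts the arm sizes in its own paragraph as well as the two later sections. A reader cannot tell when enrolment is complete.

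2. **The allocation method.** In the standard sense, simple randomisation assigns each patient independently. The arm sizes are then random, whereas the sample-size calculation treats 12 per arm as fixed. A list prepared with 12 places for each arm would deliver the planned sizes, but that is restricted randomisation and the text does not describe it. If allocation really is simple, power for the tightest comparison depends partly on chance.

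**Working it through.** **Inputs.** From Sample size, reading the first figure of each pair as the SD and the second as the expected difference:

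| Contrast with placebo | SD | Difference | Effect size |
|---|---|---|---|
| Propolis, fasting glucose (mmol/L) | 0.6 | 1.0 | 1.67 |
| Propolis, A1C (%) | 0.5 | 0.8 | 1.60 |
| Propolis, 2-h glucose (mmol/L) | 2.3 | 3.9 | 1.70 |
| Metformin, fasting glucose (mmol/L) | 2.4 | 3.0 | 1.25 |
| Metformin, A1C (%) | 1.0 | 1.5 | 1.50 |
| Metformin, 2-h glucose (mmol/L) | 3.5 | 5.5 | 1.57 |

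The type 1 error is 5% two-sided (Statistic analysis) and the target power is 80%.

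**Step 1: reproduce the plan's 12 per arm.** By the normal approximation, n per arm = 2 × (1.960 + 0.842)² / (effect size)². The smallest effect size, metformin on fasting glucose, drives the result: 2 × 7.849 / 1.25² = 10.05. Adding 20% gives 10.05 × 1.2 = 12.06, about 12 per arm, so 3 × 12 = 36. Dividing by 0.8 instead gives 12.56, or 13 per arm and 39 in total. Rounding up to 11 first and then dividing gives 14 per arm and 42 in total. None of these gives 34, which is also not divisible by 3; its nearest split is 11/11/12.

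**Step 2: what the total of 34 costs.** Power of a two-sided 5% two-sample t-test (noncentral t) for metformin versus placebo on fasting glucose, before losses:

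| Arm sizes | Power |
|---|---|
| 12 v 12 | 83.3% |
| 11 v 12 | 81.5% |
| 11 v 11 | 79.6% |

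**Step 3: arm sizes under simple randomisation.** The documents give no ratio; 1:1:1 is assumed from the equal arms. For 36 patients, P(a, b, c) = 36! / (a! b! c!) × (1/3)³⁶.

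- The SD of one arm's size is √(36 × 1/3 × 2/3) = 2.83.
- P(exactly 12/12/12) = 0.0226.
- P(all three arms between 11 and 13) = 0.147.
- P(metformin or placebo arm has 9 or fewer) = 0.371.
- P(metformin or placebo arm has 8 or fewer) = 0.21.

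**Step 4: carry this through to power.** The t-test power for metformin versus placebo on fasting glucose was averaged over all allocations, weighted by the probabilities in step 3:

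- With 36 patients, mean power is 81.0%, which is 83.3 − 81.0 = 2.3 points below 12 v 12. Power is below 80% in 39% of allocations and below 75% in 15%.
- A split of 8 v 12 gives 73.6%, and 8 v 14 gives 76.5%.
- With 34 patients, mean power is 78.4%, and 56% of allocations are below 80%.

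The other five active-versus-placebo contrasts have 87.4% to 94.0% power even at 8 v 12.

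**Step 5: check against the planned test.** The plan compares pairs of arms by Mann-Whitney after a significant Kruskal-Wallis test: "with those that will be significant a post-hoc test (Mann Whitney U) will be performed". A simulation of the Mann-Whitney test (exact critical values, normal data, 40,000 replicates per pair of arm sizes, Kruskal-Wallis step not modelled) gave 79.7% at 12 v 12 and a mean of 77.5% over allocations of 36. That is a loss of about 2.1 points on unrounded values, close to the t-test result.

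**The case against.** The strongest reply is that little follows from either point. The plan claims only about 36 patients and about 80% power, and 79.6% to 81.5% at 34 is consistent with that. Simple randomisation is valid and unbiased, rank tests do not need equal arms, and the 2.3% chance of exact equality does not measure harm. A numbered list with 12 places per arm is also a natural reading of a paragraph that names both a list and three arms of 12, and under that reading none of the imbalance figures apply. Expected losses matter more than imbalance: at 10 v 10 the same t-test gives 75.3%, which is 8.0 points below 12 v 12, against 2.3 points for imbalance on average. Finally, 34 might be a count of patients achieved or completing, since the arm sentence is in the past tense.

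Much of this stands as a limit on size. The average cost is small, it is conditional on the method being truly simple, and power before losses overstates the plan's working power. The figures also cover only contrasts with placebo; propolis versus metformin is planned but not powered. The objection does not remove the defect. No text identifies 34 as a completer count; the sentence is prospective, and 20% loss from 36 would leave about 29 (36 × 0.8 = 28.8). The word approximately does not let 34 patients fill three arms of 12. A 12-per-arm list, if there is one, is not what the protocol describes.

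**Conclusion.** The concern holds. The number to be randomised is stated two ways, and the plan's own inputs support 36. Simple randomisation, as named, does not guarantee the arm sizes behind the sample-size calculation.

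The discrepancy in the total is two patients. The allocation point is a tail risk for one powered contrast, metformin versus placebo on fasting glucose, and does not threaten validity. The imbalance figures assume a 1:1:1 ratio and independent assignment; the power figures assume the stated SDs and differences, normal data and no losses. If a list with 12 places per arm is already in use, the allocation point is one of wording only. The correction should still be made, because the enrolment target and the allocation method are core protocol items.

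**What to change.** 1. **Reconcile the total.** State 36 throughout, which agrees with the Sample size and Statistic analysis sections. If 34 is the intended number, give its arm sizes and the power at 34. If it is a count of something else, say what.

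2. **Describe the allocation as restricted.** Replace simple randomisation with a concealed 1:1:1 list that closes at exactly 12 per arm. One random ordering of 36 places, 12 per arm, would do. So would permuted blocks whose sizes sum to 36, for example six blocks of 3 and three of 6 in random order: 6 × 3 + 3 × 6 = 36, giving each arm 6 × 1 + 3 × 2 = 12. If such a list exists, keep it and describe it correctly.

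The cost is one corrected number and one sentence on how the list is generated, with no extra patients. The downside is slight predictability near the end of a block or of the list, which the double blind limits.

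### The placebo is calcined magnesia in an unstated amount, so the control arm is not established as inert for gastrointestinal tolerability

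*Combined protocol and SAP*

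**What the plan says.** The Study design section names the placebo material in one sentence: "Calcined magnesia will be used for the placebo". It gives no weight per capsule, no other ingredient and no reason for the choice. The propolis capsules are a commercial product "containing 300 mg of propolis powder", metformin is given at 850 mg twice daily, and the third group gets "12 more, placebo in the same pharmacological presentation". No excipient is listed for either active product. Exposure is the same in all arms: "All patients will receive for 12 weeks one capsule before the first bite of breakfast and another before the first bite of dinner".

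The Statistic analysis section makes this arm the reference: "The study will be designed to demonstrate the effect of propolis and metformin relative to placebo". Two of the three pairwise comparisons use it. Adverse events are checked at each visit (Clinical and laboratory measurements) and summarised descriptively in everyone who took at least one dose (Statistic analysis).

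The Selection criteria remove, among others, "Individuals with lack of tolerability to propolis, metformin and/or placebo". The Security measures section mentions information on possible adverse effects of propolis and metformin, and says nothing about the placebo material.

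**The concern.** A placebo arm shows how often events occur without the active product. That reading fails if the placebo can itself cause the events being counted. Magnesium oxide is known for antacid and laxative action. This is general pharmacology, not something the protocol states. Whether it matters here depends on an amount that the protocol does not give.

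Two things are at stake. The first is the safety summary: gastrointestinal events from the filler would raise the placebo rate and make propolis and metformin look better tolerated than they are. The second is retention: placebo patients who do not tolerate the filler fall under the elimination rule, so the reference arm could lose patients because of its own capsule content. Analysis cannot repair either one, because the planned laboratory tests do not include magnesium and no other arm has an inert control.

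**Working it through.** **Step 1. Capsule content by arm (Study design).**

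| Arm | Stated content | Magnesia stated? | Amount of magnesia |
|---|---|---|---|
| Propolis | 300 mg propolis powder, twice daily | No | Not stated |
| Metformin | 850 mg, twice daily | No | Not stated |
| Placebo | Calcined magnesia, twice daily | Yes | Not stated |

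The documents show magnesia in one arm and are silent on the other two. Silence does not prove absence. Products of 300 mg and 850 mg are to share one presentation with the placebo, and the protocol does not say how they are matched or with what filler.

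**Step 2. Effect on the tolerability comparison.** Let a be the gastrointestinal event rate in an active arm, c the rate that an inert control would have shown, and d the rate added by the filler in the placebo arm. If the active capsules contain no magnesia:

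observed difference = a − (c + d) = (a − c) − d

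The excess over an inert control is understated by d. For d > 0 the direction is fixed: the active arms look better tolerated. The documents give no value for d.

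**Step 3. Scale.** The Sample size section gives 12 per group. The Study design section gives a total of 34, although its three groups of 12 sum to 36; 12 is used here. The figure of 12 reproduces from the most demanding pair, metformin fasting glucose (SD 2.4, difference 3.0 mmol/L, two-sided 5%, power 80%):

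n = 2 × [2.4 × (1.960 + 0.842) / 3.0]² = 10.05 per arm

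With 20% loss this is 10.05 × 1.2 = 12.06, or 10.05 / 0.8 = 12.6.

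With 12 in the placebo arm, the values of d are:
- one extra patient with an event: 1/12 = 8.3 percentage points
- two: 2/12 = 16.7 points
- three: 3/12 = 25.0 points

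These figures show how coarse a group of 12 is. They do not estimate what the filler does.

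**Step 4. Elimination.** A placebo patient removed for intolerance stays in the safety summary after one dose, so that event is counted. The intention-to-treat definition also keeps such a patient if a baseline value exists. The plan does not say whether a final measurement would be taken, or how a missing one would be handled in the comparison of final data. The allowance for loss is 12 − 10.05 = 1.95, about two patients per arm. A third loss leaves 9, below the calculated 10.05 for metformin fasting glucose. The other five SD and difference pairs need 5.46 to 6.98 per arm before loss and would not be short.

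**Step 5. Contrasts reached.** Propolis versus placebo and metformin versus placebo use the magnesia arm. Propolis versus metformin does not. Its tolerability reading is affected only if the two active capsules differ in magnesia content.

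**The case against.** The strongest reply is that activity depends on dose and the dose is unknown. A small or diluted amount of magnesia may do nothing, so the plan has not been shown to use an active control. That stands, and the point claims only that inertness is not established. It also stands that the planned superiority comparisons concern effectiveness, while safety is only described. The part with a plausible mechanism therefore touches a descriptive summary, and reaches the tested comparisons only through loss of placebo patients.

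A reader might go further in four ways that the documents do not support.

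- **Glycaemic or absorption bias.** No section says that magnesia changes glucose or gives an effect size. If it did lower glucose, the placebo contrasts would shrink, which works against a superiority claim.
- **A contradiction with eligibility.** The exclusion covers "subjects who consumed drugs or supplements that modify the behavior of DM2". It conflicts with the placebo only if magnesia modifies diabetes, which the protocol does not say.
- **An admission that the placebo is active.** The elimination rule names placebo alongside the two drugs, but a double-blind trial needs a rule covering every arm, and patients can report intolerance to an inert capsule.
- **A daily magnesium dose.** If the fill weight equalled that of an active ingredient (300 to 850 mg), magnesium at 24.3/40.3 = 0.603 of the oxide would give about 362 to 1,025 mg a day from two capsules. The protocol does not support that fill weight. A mixed filler could bring the amount far lower, so the range is not used here.

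**Conclusion.** The point holds for gastrointestinal tolerability. The placebo material has known antacid and laxative action, its amount is unstated, and it is not described in either active capsule. The plan therefore gives no basis for reading the placebo arm's gastrointestinal event rate as that of an inert control. Any filler effect would flatter both active arms, by 8.3 percentage points for each additional placebo patient affected, and could lead to elimination of placebo patients.

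This rests on two assumptions that the documents neither confirm nor refute: that the amount is enough to cause symptoms, and that the active capsules contain less magnesia or none. No conclusion follows about glycaemic outcomes. The point deserves action because it can be corrected cheaply before the start and cannot be corrected afterwards.

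**What to change.** In the Study design section, before the placebo is prepared, replace calcined magnesia with a pharmacologically inert filler in capsules of identical appearance, and name the filler. The cost is re-preparing and matching one arm's supply: 12 patients × 2 capsules × 84 days = 2,016 capsules. It needs no extra patients, visits or tests.

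If the placebo has already been made, state in the same section the magnesium oxide content per placebo capsule and whether the propolis and metformin capsules contain any. Then add to the safety paragraph of the Statistic analysis section, and carry into the report, that gastrointestinal event rates in the active arms cannot be read as excess over an inert placebo. This costs only text, but it leaves the tolerability comparison unresolved.
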